8.5 Safety Follow-up Period if Device Not Removed

All patients who do not have the IDDD removed (partial or full device) will have safety follow-up visits every 6 months at the site, with the following assessments performed:

- Informed consent (at the first assessment)
- Symptom-directed PE
- Clinical laboratory tests; only if indicated for a device-related AE
- X-ray monitoring; only for migration or device-related issue
- Concomitant medications, therapies, and procedures; only if indicated for a device-related AE
- AE monitoring only for device-related events

During the 3-year safety follow-up period, the patient may have the device removed at any time, as deemed medically necessary. A post-operative evaluation, including a postoperative check of the incision and collection of safety information, should occur within 1-3 days after the IDDD explantation. An end of study safety follow-up via a phone call should be completed within 14 days after the device removal to collect safety information.

9 QUALITY CONTROL AND ASSURANCE

Training will occur at an investigator meeting or at the site initiation visit or both, and instruction manuals (eg, laboratory manuals and pharmacy manuals) will be provided to aid consistency in data collection and reporting across sites.

Clinical sites will be monitored by Shire or its designee to ensure the accuracy of data against source documents. The required data will be captured in a validated clinical data management system that is compliant with the Food and Drug Administration (FDA) 21 Code of Federal Regulations (CFR) Part 11 Guidance. The clinical trial database will include an audit trail to document any evidence of data processing or activity on each data field by each user. Users will be trained and given restricted access, based on their role in the study, through a password protected environment.

Data entered in the system will be reviewed manually for validity and completeness against the source documents by a clinical monitor from Shire or its designee. If necessary, the study site will be contacted for corrections or clarifications; all missing data will be accounted for.

SAE information captured in the clinical trial database will be reconciled with the information captured in the Pharmacovigilance database.

10 PLANNED STATISTICAL METHODS

10.1 General Statistical Methodology

This is an open-label extension of study HGT-SAN-055 to evaluate the long-term safety and clinical outcomes of intrathecal administration of HGT-1410 in patients with MPS IIIA. The statistical methodology supporting the trial will focus on descriptive rather than inferential approaches, given the early phase and objectives of this trial.

Data will be summarized by dose group (10 mg, 45 mg, and 90 mg) with respect to demographic and baseline characteristics, efficacy variables, and safety variables. Summary statistics for continuous variables will include the n, mean, standard deviation, median, minimum and maximum. Categorical variables will be summarized in a contingency table by the frequency and percentage of patients in each category. Data will be plotted to assess trends across time as appropriate.

No a priori hypotheses will be tested. Exploratory hypotheses may emerge from the data analysis, in which case, appropriate testing methods will be applied and specified in the statistical analysis plan.

There are no formal hypotheses associated with the evaluation of the safety and performance of the IDDD device (SOPH-A-PORT Mini S). All analyses of device safety and performance will be descriptive and no statistical testing will be performed. Device related analyses will be based on patients for whom the device implant procedure was performed and are described in the sections below.

10.2 Determination of Sample Size

Since this is an extension study, sample size is determined by the number of patients who completed HGT-SAN-055 (maximum of 12 patients) and elected to continue treatment with HGT-1410 in this study. Hence no statistical estimation of the sample size was performed.

10.3 Analysis Populations

The primary analysis population consists of all eligible patients from HGT-SAN-055 who have agreed to participate in the extension study. This population will be used to perform both safety and efficacy analyses. The collection of detailed data pertaining to the SOPH-A-PORT mini S will permit device-related analyses to be conducted in the subset of patients in the primary analysis population who had the SOPH-A-PORT Mini S implant procedure performed.

10.4 Demographics and Baseline Characteristics

Patient disposition for those enrolled will be presented in a summary table using number and percentage of patients enrolled, completed or discontinued/withdrew. The reasons for discontinuation/withdrawal will also be presented.

Demographic and baseline characteristics (eg, age, race, ethnicity, medical history, and surgical history) will be reported in summary tables.

10.5 Statistical Analysis of Pharmacokinetic Variables

Not applicable.

10.6 Efficacy, Safety, and Pharmacodynamic Evaluations

10.6.1 Primary Analyses

10.6.1.1 Safety Analysis

In general, safety assessments will be based on all assessments post-baseline. The assessment of safety will be based primarily on the frequency of AEs, and on the frequency of clinically notable abnormal vital sign and laboratory values. Changes from baseline will be calculated by subtracting the baseline value from the post-baseline value.

All enrolled patients who had an IDDD surgical procedure and/or received administration of HGT-1410 will be included in the safety analysis.

Adverse events will be recorded throughout the study and at early termination. Adverse events and medical conditions will be coded using the Medical Dictionary for Regulatory Activities (MedDRA).

Adverse events will be summarized by presenting, for each dose group during the treatment period, the number and percentage of patients having any AE, having an AE in system organ class, and having each individual AE. In addition, those events which resulted in death or were otherwise classified as serious will be presented in a separate listing. The incidence of treatment-emergent adverse events, defined as all AEs from the time of the surgery for IDDD implantation to the last follow up contact, ie, 30 days after the last HGT-1410 administration, (new or worsened from baseline) during the treatment period, will be summarized by system organ class, severity, type of adverse event and relationship to trial medication/procedure.

Treatment-emergent AEs, of the treatment period, deemed related to HGT-1410 administration will be summarized separately.

IDDD and procedure-related AEs will be summarized within system organ class by preferred term. IDDD and procedure-related AEs will be tabulated by severity (mild, moderate, severe) and degree of relatedness. Separate tabulations will be provided for adverse events related to the IDDD, device surgical procedure (including post-implant infections) and IT administration process. These summaries will be presented by device and overall, as appropriate.

Descriptive summaries of clinical laboratory evaluations (hematology, serum chemistry, urinalysis and CSF) results will be presented in summary tables by evaluation visit. Changes from baseline will be summarized for each post-baseline visit. Each laboratory result will be categorized as a patient having had (1) an Abnormal and Clinically Significant (CS) value at any time, (2) no CS values at any time but had at least one Abnormal and not CS (NCS) value, and

(3) no CS or NCS values at any time; the number and percentage in each category will be presented. For any patient who experiences a CS laboratory result at any time that was not CS at baseline (or the most recent non-missing value prior to the start of the treatment), their entire profile for that particular laboratory parameter will be presented as a listing.

The observed values and changes from baseline for vital sign data will be summarized for each dose group. Shift tables may be presented, utilizing reference ranges. Patients with notably abnormal values will be identified and listed separately along with their values.

The observed values and changes from baseline for ECG data will be summarized for each dose group. Patients with any clinically significant findings and/or conduction abnormalities will be listed separately along with their values.

Anti-rhHNS antibody formation will be monitored throughout the study. Results will be presented in summary tables by number and percentage of positive and negative specimens by evaluation visit, and number and percentage of positive and negative specimens overall. The effect of antibodies on other safety parameters will be assessed by presenting summary tables by antibody status.

For those patients who fail to complete the study, the reason for discontinuation will be listed by patient and dose group.

Listings of all study safety data will be presented.

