4.3 Study Duration and Dates

The study duration allows patients who completed Study HGT-SAN-055 and elected to continue treatment with HGT-1410 in Study HGT-SAN-067 to receive treatment with HGT-1410 up to 8 years.

Patients with a partial or full device still in place after completion of the treatment period, may be followed for safety up to an additional 3 years or until the device is removed in the last patient.

The LPLV will be the safety follow-up visit after the final device (partial and/or full) is removed from the last patient during the safety follow-up period.

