10.6.2 Other Observations Related to Safety

10.6.2.1 IDDD Performance

IDDD safety and performance will be summarized in detail for patients implanted with the SOPH-A-PORT Mini S. Difficulties associated with the implant procedure (e.g. excessive bleeding, CSF leakage, etc.) will be summarized. A summary of abnormal findings from the IDDD radiological assessments will also be presented.

The proportion of patients with at least one IDDD failure and/or malfunction, as well as the number of and reasons for IDDD failures/malfunctions will be summarized. The rate of IDDD failures/malfunctions and 95% confidence interval will also be estimated. The time from initial implant surgery to first IDDD failure and/or malfunction will be summarized. Patients without an IDDD failure/malfunction will be censored at their last study drug injection date. A by-patient listing of the device failure/malfunction data will be displayed.

The proportion of patients for whom a successful first injection of study drug occurred will be reported among those for whom a first injection was attempted (i.e. those who had an apparently successful implantation and did not suffer a device removal or revision prior to first scheduled injection). The proportion of patients who had no failed injection attempts during the study will also be summarized. The corresponding 95% confidence intervals of the proportion of interest will be estimated, where appropriate. Injections not given for patient reasons (e.g. patient uncooperative, competing medical issue, etc.) will not be included in the determination of these success proportions.

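### Adverse events are summarised only as the percentage of patients ever affected over up to 8 years; event rates per unit of exposure should stand beside it

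*Protocol*

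**What the plan says.** Section 10.6.1.1 (Safety Analysis) sets the basis of the safety assessment, which is AE frequency together with notable vital sign and laboratory findings: "The assessment of safety will be based primarily on the frequency of AEs, and on the frequency of clinically notable abnormal vital sign and laboratory". For each dose group during the treatment period, the AE summary is "the number and percentage of patients having any AE, having an AE in system organ class, and having each individual AE". The incidence of treatment-emergent AEs (TEAEs) "will be summarized by system organ class, severity, type of adverse event and relationship to trial medication/procedure", and those "deemed related to HGT-1410 administration will be summarized separately". Deaths and serious events are listed. AEs related to the device, the device surgery and the intrathecal (IT) administration process are tabulated separately, by device and overall as appropriate.

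Section 4.3 allows patients "to receive treatment with HGT-1410 up to 8 years". Under section 7.26 a patient may leave at any time and is not replaced.

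For the implanted delivery device (IDDD), section 10.6.2.1 is more specific: "The rate of IDDD failures/malfunctions and 95% confidence interval will also be estimated", with time to first failure or malfunction and a censoring rule. No rate, patient-time denominator or time to first event is named for AEs.

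**The concern.** The primary objective (section 2.1) is long-term safety and tolerability, and AEs are the first of the five safety endpoints in section 3.1. An ever-affected percentage suits short follow-up of similar length in all patients. Here follow-up may run to 8 years and can differ between patients.

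The protocol's own definitions make frequent events likely. Section 7.22.1.1 counts intercurrent illness and worsening of existing conditions as AEs, section 7.2 makes any change from the screening examination an AE, and section 1 describes the disease as progressive. A child with one event and a child with twenty count the same.

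Exposure is also unequal by design in two places. The SOPH-A-PORT enters only as a replacement after Amendment 4 (section 6.1.2), so the two devices have different time at risk. Group 1 moved from 10 mg to 45 mg (section 6.2), while section 10.1 keeps the summaries by 10, 45 and 90 mg. At stake is whether the main AE table can describe how often events occurred on each dose and each device.

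**Working it through.** The protocol states no figure to reproduce here: section 10.2 says "Hence no statistical estimation of the sample size was performed", and no background AE rate is given.

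**Inputs**
- Duration: Month 102 − Month 6 = 96 months, and 96/12 = 8.0 years, which agrees with section 4.3.
- Event rate r per patient-year: assumed, 0.02 to 1.
- Patients: at most 12 in three dose groups (sections 10.1 and 10.2). Group sizes are not given, so 4 per group is assumed where needed.

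**Formula.** With a constant rate, P(ever affected by time T) = 1 − exp(−rT).

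**Saturation at T = 8 years, and the effect of doubling the rate**

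| r per patient-year | Ever affected | If rate doubles | Change (points) |
|---|---|---|---|
| 0.02 | 14.8% | 27.4% | 12.6 |
| 0.05 | 33.0% | 55.1% | 22.1 |
| 0.1 | 55.1% | 79.8% | 24.7 |
| 0.25 | 86.5% | 98.2% | 11.7 |
| 0.5 | 98.2% | 99.97% | 1.8 |
| 1 | 99.97% | about 100% | 0.03 |

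The percentage passes 95% when r exceeds −ln(0.05)/8 = 0.37 per patient-year, and 99% when r exceeds −ln(0.01)/8 = 0.58.

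**Follow-up, same rate and no drug effect.** At r = 0.25, T = 2 gives 1 − exp(−0.5) = 39.3% and T = 8 gives 1 − exp(−2) = 86.5%. At r = 0.1 the figures are 18.1% and 55.1%.

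**Repeat events.** Four patients for 8 years give 32 patient-years. At r = 0.5 the expected count is 16 events, rising to 32 if the rate doubles. The expected number of patients affected goes from 4 × 0.982 = 3.93 to 4 × 0.9997 = 4.00.

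**Precision of a rate on 32 patient-years (exact Poisson 95% intervals).** With 32 events the rate is 1.00, interval 0.68 to 1.41. With 3 events it is 0.09, interval 0.02 to 0.27. These intervals treat all events as independent, so they are too narrow if children differ in their underlying rate.

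**The case against.** The best objection is that section 10.6.4 leaves the final analyses and presentations to the SAP, which is not shown, and exposure-adjusted AE tables are often specified there. That stands in part: nothing in the protocol excludes such rates, and their absence alone would be no error. But the protocol is not silent. It states the AE measure, and it specifies a rate and a censored analysis for device failures only. The stated measure can therefore be judged against the stated objective.

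A reader might infer that the whole AE summary approaches 100% in every dose group. It does not. The same sentence covers each system organ class and each individual AE, and uncommon rows stay well below 100% and respond to a change in rate.

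A reader might also infer that the plan cannot show a difference in risk. That is too strong. Severity and relatedness splits, the serious-event listing and full safety listings keep information, and with at most 12 patients repeat events can be read from those listings. Disposition (section 10.4) and discontinuation reasons by dose group show early leaving.

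Nor does a power comparison between percentages and rates make the case. Section 10.1 says "No a priori hypotheses will be tested". Very small groups limit any comparison of percentages at every event rate, and a simple Poisson test ignores variation between children.

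Finally, no document reports that drop-out differed by dose. The TEAE window also opens at device implantation surgery, so time in HGT-SAN-055 can fall inside it. A contrast that counts extension time alone would overstate the imbalance.

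**Conclusion.** The point holds in a limited form. The only AE measure that section 10.6.1.1 names is poorly suited to long-term follow-up. For the any-AE row, and for other events at about 0.5 per patient-year or more, it is near 100% whatever the drug does. It ignores repeat events, and it is not comparable between dose groups or devices with unequal follow-up. Rows for uncommon events remain informative.

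The size rests on assumed constant event rates. The dependence on follow-up does not rest on any particular rate. Unequal time by device and by dose received follows from the protocol itself; unequal drop-out between dose groups is possible but not documented. This is an improvement worth making to a descriptive plan, and it does not invalidate the safety analysis.

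**What to change.** Keep the percentages. Beside them in section 10.6.1.1, name:
- AE counts and first events per patient-year, with injections as the denominator for IT-administration AEs and device-years for IDDD AEs;
- 95% confidence intervals that allow for between-patient variation, for example from a patient-level variance or a negative binomial model;
- presentation overall, by treatment year, by device and by dose actually received, with Group 1 patient-time split at the change from 10 mg to 45 mg. Without that split, 45 mg exposure would be credited to the 10 mg group;
- patient-time counted over the same window as the TEAE definition, so that numerator and denominator match.

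No new data are needed: injection dates (section 6.3.1) and AE onset dates (section 7.22.5.2) are already recorded. The cost is protocol or SAP wording and a few extra tables. Intervals will be wide with at most 12 patients, and variance estimates within single dose groups will be unstable, so the overall and by-year rates will be the most useful. The by-year table also checks whether a constant rate is a fair summary.

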3 STUDY ENDPOINTS

3.1 Primary Endpoint

The primary endpoints of this study are related to the long-term safety of intrathecal HGT-1410 administration. The safety endpoints are:

[figure not shown]
- adverse events (type and severity)
- changes in clinical laboratory testing (serum chemistry including liver function tests, hematology, and urinalysis)
- electrocardiograms (ECG)
- CSF chemistries (including cell counts and inflammatory markers)
- anti-rhHNS antibodies (in CSF and serum).

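### The three-class laboratory table counts any abnormal value at any time, with no reference to baseline status or number of draws, so it mixes chance and pre-existing abnormalities with new ones

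*Protocol*

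**What the plan says.** Section 3.1 of the protocol makes laboratory change a primary endpoint: "changes in clinical laboratory testing (serum chemistry including liver function tests, hematology, and urinalysis". Section 10.6.1.1 rests the safety assessment primarily on adverse event frequency and "on the frequency of clinically notable abnormal vital sign and laboratory values".

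The same section then fixes the laboratory classes:

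- Class 1 takes every patient with "an Abnormal and Clinically Significant (CS) value at any time".
- Class 2 takes those who have "no CS values at any time but had at least one Abnormal and not CS (NCS) value".
- Class 3 takes the remainder, described as "no CS or NCS values at any time; the number and percentage in each category will be presented".

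Three other statements in 10.6.1.1 bear on how this table is read:

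- The general rule at its start: "In general, safety assessments will be based on all assessments post-baseline".
- The visit-wise analysis: "Changes from baseline will be summarized for each post-baseline visit".
- A full profile listing for patients who become CS: "For any patient who experiences a CS laboratory result at any time that was not CS at" (the sentence goes on to name the pre-treatment value as the reference).

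Treatment-emergent adverse events in that section must be new or worse than at baseline, and vital signs may be given shift tables. The laboratory classes have neither feature.

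**The concern.** Classes 2 and 3 differ by a single value over up to eight years of sampling. A maximum over many draws rises with the number of draws even if nothing happens to the patient. The split between these two classes may therefore reflect the width of the reference range and the amount of sampling more than the drug.

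The rule also has no baseline column. A patient whose value was abnormal before treatment and stays abnormal falls in the same class as one who was normal and became abnormal on treatment. In class 1, likewise, a patient already CS at baseline and still CS is counted with newly CS patients.

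This is the only laboratory frequency table that the protocol plans, and 10.6.1.1 gives such frequencies a leading role. With at most 12 patients in three dose groups, a few misplaced patients change the picture.

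**Working it through.** The protocol states no draw count or expected frequency, so there is no figure of its own to reproduce.

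**Draws**

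- Doses are given every 28 days (6.3), over up to 8 years of treatment (4.3), which is Month 6 to Month 102.
- Hematology, chemistry and urinalysis are taken before each dose to Month 54, then every 3 months (8.2.1.1). Months 6 to 54: 48 × (365.25/12)/28 = 52.2, so 52. Months 57 to 102 in steps of 3: 16. Total 52 + 16 = 68.
- CSF is sampled before every injection (6.3.1): 96 × (365.25/12)/28 = 104.4, so 104.
- Counting calendar months plus the end-of-study visit gives 48 + 16 + 1 = 65 and 96 + 1 = 97. Counting from the first dose in HGT-SAN-055 adds about 6 or 7.

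**Chance of at least one out-of-range value, one parameter, no drug effect**

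Independent draws: P = 1 − (1 − p)^n. For p = 5% and n = 68, P = 1 − 0.95^68 = 96.9%.

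Correlated draws: X = √ρ·b + √(1 − ρ)·e, with b (patient) and e (draw) standard normal. The range is ±c, where c is set so that a single draw is outside with probability p. Then P = 1 − E[Pr(|X| < c given b)^n], where the expectation is over patients.

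| p per draw | ρ | 68 draws | 104 draws |
|---|---|---|---|
| 5% | 0 | 96.9% | 99.5% |
| 5% | 0.5 | 69.2% | 78.5% |
| 5% | 0.7 | 44.6% | 50.4% |
| 5% | 0.9 | 20.7% | 22.5% |
| 1% | 0 | 49.5% | 64.8% |
| 1% | 0.7 | 14.3% | 17.0% |
| 1% | 0.9 | 5.7% | 6.4% |

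Both p and ρ are assumptions; p = 5% corresponds to a central 95% reference range. Among 12 patients with 68 draws, the expected number with at least one such value is 12 × 0.969 = 11.6 for p = 5% and ρ = 0. It is 12 × 0.446 = 5.4 for p = 5% and ρ = 0.7, and 12 × 0.143 = 1.7 for p = 1% and ρ = 0.7.

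**Does the baseline value itself matter?** At p = 5% with independence, 69 draws give 97.1% and 68 give 96.9%. One extra draw makes almost no difference.

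**Pre-existing against new abnormalities**

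| Baseline | On treatment | Class | In the CS listing? |
|---|---|---|---|
| Normal | Abnormal, not CS | 2 | No |
| Abnormal, not CS | Unchanged | 2 | No |
| Normal | CS | 1 | Yes |
| CS | Still CS | 1 | No |

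The listing separates the last two rows. No planned count separates the first two.

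**The case against.** The strongest reply is that the analysis of change lies elsewhere. Change from baseline is summarized at every post-baseline visit. Newly CS patients have their full profile listed, and all safety data are listed for at most 12 patients. Section 7.22.1.1 also allows laboratory shifts that the investigator considers important to be recorded as adverse events. This stands, and it confines the defect to one table. It does not repair that table: visit means in very small groups can hide one patient's shift, and the CS listing omits patients who go from normal to abnormal but not CS.

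The reply continues that 10.6.4 leaves final presentations to the SAP. That is fair for table layout, but the classification rule is stated in the protocol and is not an omission.

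Four stronger readings are tempting, and the documents do not support them:

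- That baseline values count towards the classes. The text does not say so, and the general post-baseline rule points the other way. The wording is at most ambiguous, and the numerical effect is negligible.
- That the plan cannot show laboratory change under treatment. The visit-wise changes and the listing contradict this.
- That a real shift, for example in liver tests, would leave the table unmoved. A shift judged CS moves a patient not already there into class 1. Chance out-of-range values mainly affect the split between classes 2 and 3.
- That dose groups with shorter follow-up will look safer. Class membership does depend on the number of draws, and patients who leave are not replaced (7.26). But all groups share one schedule, and no difference in follow-up between them is documented.

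**Conclusion.** The point holds for this one table. As written, it cannot separate new from pre-existing abnormalities, and normal variation alone can move many patients from class 3 to class 2.

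The size is uncertain because neither the reference-range coverage nor the within-patient correlation is in the protocol. For one parameter over 68 draws, the chance of at least one out-of-range value is about 97% at 5% per draw with independence, about 45% at correlation 0.7, and about 14% at 1% per draw and correlation 0.7. It falls to about 6% if 1% per draw is combined with correlation 0.9. The failure to separate pre-existing from new abnormalities depends on none of these assumptions; it follows from the wording.

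The primary laboratory endpoint is still analyzed through change from baseline. This is a correction to a stated rule and does not undermine the safety analysis as a whole.

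**What to change.** Amend 10.6.1.1, or carry the following into the SAP:

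- State that the three classes use post-baseline values only.
- Cross-tabulate them by baseline class (normal, abnormal but not CS, CS), so that new or worsened abnormalities are counted apart from pre-existing ones.
- Show the number of draws or patient-years beside each count.
- Keep the listing of newly CS patients.

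A table of the worst value per year is not a safe substitute unless it allows for the drop in blood and urine sampling after Month 54. Before that month there are about 13 draws a year, afterwards 4. At 5% per draw with independence, the yearly chance of an out-of-range value falls from 1 − 0.95^13 = 49% to 1 − 0.95^4 = 19%, which would look like an improvement that did not occur.

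The cost is wording and somewhat more table work, with no new samples or visits. With at most 12 patients, many cells of the cross-tabulation will be sparse.
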